The proposed study will examine physiologic responses to acute psychological challenge in the laboratory among healthy adults. It is widely accepted that there is an increase in circulating markers of inflammation following a single bout of laboratory stress. This increase in systemic inflammation is believed to contribute to the damaging health effect of psychological stress. However, to date the biological mechanisms by which psychological stress is transduced into inflammation are unclear. Our preliminary evidence suggests that mitochondrion may play a role, with stress-induced increases in circulating levels of mitochondria- derived signaling molecules that are known to modulate immune cell function and the production of pro-inflammatory cytokines.

To test this possibility, we plan to conduct a crossover experimental trial examining physiological responses to an evaluative speech task under laboratory conditions. We have previously used this task to induce physiological arousal. We plan to recruit 60 non-smoking volunteers (50% female, aged 20-50 years) and test them on two occasions separated by at least a month. On one occasion they will be exposed to the speech task. On the other occasion, they will rest quietly for the same period. Conditions will be counterbalanced. At both visits cardiovascular responses (heart rate, blood pressure, and heart rate variability) will be assessed as measures of autonomic activation before, during and after the task period. Participants will also have an intravenous catheter inserted and blood drawn at ten time points over the two-hour testing period on each occasion. Blood samples will be sent to laboratories at the University of Pittsburgh and at Columbia University for the assessment of mitochondria-derived signalling molecules, inflammatory markers, cortisol and catecholamine levels.

Study Objectives

Our overarching hypothesis is that psychosocial stress regulates ccf-mtDNA release, which, in turn, signals a proinflammatory response. We examine this hypothesis in parallel human and cell-based studies. The current Clinical Trial only covers Aim 1 of the parent grant, which is the human study.

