We propose a crossover experimental trial examining physiological responses to a socio-evaluative speech task under laboratory conditions. Participants will be tested on two occasions separated by at least 1 month. On one occasion, they will be exposed to the speech task. On the other occasion, they will rest quietly for the same period of time with identical assessment in the absence of the stressor. This control session will allow us to assess and control for any possible effects of the passage of time (e.g., circadian variation in cortisol levels), simply being assessed (e.g., discomfort), and the intravenous catheter. Conditions will be counterbalanced in randomized starting order across subjects and blood drawn at ten time points over two hours to assess ccf-mtDNA, markers of inflammation (IL-6 and TNF- α), and levels of cortisol, epinephrine and norepinephrine. Heart rate (HR), blood pressure (BP), and heart rate variability (HRV) will be assessed as indices of autonomic activation before, during and after the stressor. The speech task is a widely used, highly effective way to investigate stress responses in a laboratory setting. It induces significant increases in cortisol, indices of autonomic activation, and circulating IL-6 and TNF α . Our preliminary data provides novel evidence that this stressor also results in increased cc-mtDNA, which may mediate the increases in circulating levels of IL-6 and TNF- α that peak 40-90 minutes post-stress.

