8. Current smokers (defined as having smoked a cigarette in the previous 3 months).
9. Current illicit drug use (defined as reported use of illicit drugs such as marijuana, cocaine or heroin in the previous 3 months).
10. Not fluent in English (have used English in everyday speaking and reading for at least 10 years)
11. Unable or unwilling to give informed consent
12. Unwilling to abstain from alcohol and vigorous exercise for 24 hours, from food and drinks (other than water) for 3 hours and from non-prescription medications (other than oral contraception) for 2 days prior to testing.

Statistical Considerations

For the primary analysis in Aim 1, because we are utilizing a “matched” design (in which each subject serves as his/her own control), we base our power calculations on a simple paired t-test since power formulas are not available for complex models such as the ones we propose to apply to our data. We find that with the proposed sample size $n = 60$, we have 80% power to detect a normalized difference (in terms of Cohen’s d) as small as 0.38. Combined effects sizes from a meta-analysis of the literature [1] yield normalized effect sizes for IL-6 and TNF- α at 0.35 and 0.28, respectively. For ccf-mtDNA, our pilot data give an estimated effect size of 1.13 (see Fig. 4), such that we will be sufficiently powered to detect stress-induced changes, and to detect statistically significant differences in ccf-mtDNA separately in women and in men. In fact, however, we will not have to rely on such a simple analysis, since we are collecting several measurements over time and will be modeling the entire trajectory. With multiple observations, by taking into account necessary covariates and accounting for the correlation structure among repeated observations, we will increase the power of the analysis to detect a change, potentially dramatically, and so we expect to be amply powered. For the secondary analyses, again we will be applying more sophisticated and powerful analyses, but for reference we base our power calculations on Pearson’s correlation analysis and find that with the proposed sample size we are powered to detect a “true” correlation coefficient as small as 0.35 (in absolute value), typically considered somewhere between a “small” and “medium” effect size.

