Univariate and descriptive analysis will be performed on all dependent variables and, if necessary, normalizing and/or variance stabilizing transformations will be applied to the data before inferential analyses are undertaken. All hypothesis testing will involve two-sided alternative hypotheses with the α level set to 0.05. The analytic strategy for addressing Aim 1 will involve fitting linear mixed models, which allow flexible covariance structures to account for correlation of repeated measures data. Specifically, subject and day (nested within subject) will be the random effects, and condition (stress/control) along with other covariates will be the fixed effects. We will also include time and time 2 (squared) as fixed effects to allow for a nonlinear response. The outcome variables will be the various physiological and psychological responses:

IL-6, TNF- α , ccf-mtDNA, cortisol, epinephrine, norepinephrine HR, BP, momentary negative affect, and HRV.

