## Statistical Plan and Power

Power: For the primary analysis, because we are utilizing a “matched” design (in which each subject serves as his/her own control), we based our power calculations on a simple paired t-test since power formulas are not available for complex models such as the ones we propose to apply to our data. We determined that with the sample size  $n = 60$ , we would have 80% power to detect a normalized difference (in terms of Cohen’s  $d$ ) as small as 0.38. Combined effects sizes from a meta-analysis of the literature [1] yield normalized effect sizes for IL-6 and TNF- $\alpha$  at 0.35 and 0.28, respectively. For ccf-mtDNA, our pilot data gave an estimated effect size of 1.13. Thus, with a sample of  $N=60$ , we were sufficiently powered to detect stress-induced changes. In fact, the collection and modelling of multiple measurements over time. With multiple observations, accounting for the correlation structure among repeated observations, we would increase the power of the analysis to detect a change.

Univariate and descriptive analysis will be performed on all dependent variables and, if necessary, normalizing and/or variance stabilizing transformations will be applied to the data before inferential analyses are undertaken. All hypothesis testing will involve two-sided alternative hypotheses with the  $\alpha$  level set to 0.05. The analytic strategy for addressing the laboratory stress session will involve fitting linear mixed models, which allow flexible covariance structures to account for correlation of repeated measures data. Specifically, subject and day (nested within subject) will be the random effects, and condition (stress/control) will be the fixed effects. We will also include time and time $^2$  (when indicated) as fixed effects to allow for a nonlinear response. The outcome variables will be the various physiological and psychological responses: IL-6, TNF $\alpha$ , ccf-mtDNA, cortisol, epinephrine, norepinephrine HR, BP, momentary negative affect, and HRV.

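### The claim that ten samples per session will raise power is not supported for IL-6 and TNF-alpha by the model as written, which has no condition-by-time term

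*Protocol*

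**What the plan says.** In Statistical Considerations the protocol explains that "we base our power calculations on a simple paired t-test", on the ground given as "since power formulas are not available for complex models such as the ones we propose to apply to our data". With n = 60 it reports 80% power at d = 0.38. It cites meta-analytic effects of 0.35 for IL-6 and 0.28 for TNF-alpha and a pilot effect of 1.13 for ccf-mtDNA. It then argues that the whole trajectory will be modelled from several measurements, so that "we will increase the power of the analysis to detect a change, potentially dramatically, and so we expect to be amply powered".

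The SAP (Statistical Plan and Power) drops the stronger words. It still calls N = 60 sufficient to detect stress-induced changes, and adds: "With multiple observations, accounting for the correlation structure among repeated observations, we would increase the power of the analysis to detect a change".

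The model is described in the same sections. In the protocol's words, "subject and day (nested within subject) will be the random effects", with condition and other covariates as fixed effects, plus time and time squared. The SAP repeats this without the other covariates and includes time squared only when indicated. Neither document writes a condition-by-time term.

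Under Study Design & Methods, blood is drawn at −5 min and at 5, 10, 20, 30, 45, 60, 75, 90 and 120 min after the task. The same section describes IL-6 and TNF-alpha increases "that peak 40-90 minutes post-stress". The preliminary-work text in Scientific Background puts the inflammatory peak at one to two hours.

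**The concern.** Both cytokine effects lie below the detectable effect the plan reports. The sentence on multiple observations is therefore all that takes the protocol from d = 0.38 to ample power for these outcomes. No within-session correlation, response profile or mixed-model calculation accompanies it.

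Each participant has one condition per day, and the time terms are common to both conditions. A condition effect in such a model compares whole-session averages. Extra samples reduce the noise within a session but leave day-to-day variation untouched. Samples taken when cytokines have not responded, including the one before the task, pull the average difference towards zero.

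IL-6 and TNF-alpha are central to Aim 1. If their condition effect came out non-significant in a study described as amply powered, it could be taken for absence of an inflammatory response when the test had limited power to show one.

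**Working it through.** **Inputs.** n = 60 ("We plan to recruit 60 non-smoking volunteers"). Two-sided α = 0.05 ("All hypothesis testing will involve two-sided alternative hypotheses with the α level set to 0.05"). Effects 0.35, 0.28 and 1.13, ten samples per session and the model terms are as described above. Two inputs are not in the documents and are assumed over ranges:
- ρ, the day-level share of within-person variance, = day variance / (day + residual variance);
- the response profile, summarised by f, the mean over the ten samples of the response as a fraction of its peak.

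I also assume that the cited d applies to the stress-minus-control difference at a single in-window sample.

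**1. The plan's own figure.** Exact paired-t power (noncentral t, 59 df, noncentrality d√60) at d = 0.38 is 82.5%. The effect detectable with 80% power is 0.368. The stated figure is slightly conservative, and nothing below depends on the gap.

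**2. The cytokine effects on the same test.** d = 0.35 gives 76.0%; d = 0.28 gives 56.9%.

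**3. What the written model tests.** With complete data and random subject and day intercepts, the condition estimate is the mean over subjects of (stress session mean − control session mean), with the standard error of a paired t-test on those means. Fitting the model to six simulated balanced datasets gave the same estimates, and test statistics that agreed to about three decimals (for example 2.2299 and 2.2298). So for this contrast a power formula does exist.

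**4. Effective d for that test.** Averaging multiplies the effect by f and the standard deviation by √(ρ + (1−ρ)/10):

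d_session = d × f / √(ρ + (1−ρ)/10)

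This equals d when ρ = (f² − 0.1)/0.9. Below that break-even value the written test beats the single-sample t-test; above it, it does worse. The square root is 0.529 at ρ = 0.2 and 0.742 at ρ = 0.5.

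| Response profile | f | Break-even ρ | IL-6 power, ρ = 0.2 | IL-6, ρ = 0.5 | TNF-alpha, ρ = 0.2 | TNF-alpha, ρ = 0.5 |
|---|---|---|---|---|---|---|
| 45–90 min only (4 of 10) | 0.40 | 0.067 | 52% | 30% | 36% | 21% |
| 45–120 min only (5 of 10) | 0.50 | 0.17 | 71% | 44% | 52% | 30% |
| Linear ramp to 45 min, sustained to 120 | 0.64 | 0.34 | 90% | 63% | 73% | 45% |
| All nine post-task samples | 0.90 | 0.79 | 99% | 90% | 95% | 73% |

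Example: IL-6, first row, ρ = 0.5: 0.35 × 0.40 / 0.742 = 0.189, power 30%. A 20,000-replicate simulation of this case gave 29.9%. In the ramp row f is rounded from 0.644; unrounded, break-even is 0.35 and IL-6 power at ρ = 0.5 is 64%.

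**5. ccf-mtDNA.** Even on the 4-of-10 profile at ρ = 0.5, 1.13 × 0.40 / 0.742 = 0.61, with power above 99% in the full sample.

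**6. Tests that use the time course (4-of-10 profile).**
- Mean of the four in-window samples, d / √(ρ + (1−ρ)/4), at ρ = 0.5: 0.35/0.791 = 0.443, power 92% (IL-6); 0.28/0.791 = 0.354, power 77% (TNF-alpha).
- Condition-by-time and condition-by-time-squared, 2 df, approximate noncentrality 60 × d² × 1.635/(1−ρ), where 1.635 is the part of the profile's sum of squares captured by linear and quadratic time: IL-6 about 97% at ρ = 0.3 and 99% at 0.5; TNF-alpha 85% and 95%. This treats residuals within a session as independent.

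**The case against.** A reader might infer that ten samples make power for the cytokines fall. The documents do not support that as a general statement. They give neither ρ nor the response shape, and a peak at 40–90 min does not mean no response at other times. For a ramp sustained to 120 min the written test gains power up to ρ of about 0.34, and for a response in all nine post-task samples up to 0.79. The protocol itself claims only a potentially dramatic gain.

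The meaning of d is also open, because the plan does not say whether 0.35 and 0.28 are differences at one sample or changes from baseline. If they are baseline-corrected changes, break-even for the 4-of-10 profile solves 2(1−ρ)(0.16) = ρ + (1−ρ)/10, giving ρ = 0.22/1.22 = 0.18 instead of 0.067.

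The identity with the paired t-test needs complete data and random-intercept covariance. Missing samples, time-varying covariates or another of the flexible covariance structures the plan mentions would break it. Nor can one say that covariates add nothing: person-level ones cancel in this contrast, but session-level ones such as visit order need not.

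The strongest point is that modelling the entire trajectory suggests condition-specific curves. If those were intended, the claim of a gain is largely right for a transient response, as the last step of the working shows. All of this stands and limits the conclusion. It does not rescue the power claim, because the term that would deliver the gain is written in neither document.

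**Conclusion.** The claimed gain is unsupported for IL-6 and TNF-alpha under the model as written. What follows from the plan's own test and effects is 76% and 57% power, not ample power. Under the assumptions stated (complete data, random intercepts, d referring to a single in-window sample), the written test has less power than this when ρ exceeds a break-even value, and more below it. That value ranges from about 0.07 to 0.79 over the profiles tried. At ρ = 0.5, IL-6 power is 30%, 44%, 63% and 90% across the four profiles.

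It would go too far to conclude that power necessarily falls, or that the trial as a whole is underpowered: the ccf-mtDNA comparison is safe in the full sample. The defect is a missing model term, together with a power statement that relies on it.

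**What to change.** 1. In the protocol's Statistical Considerations and the SAP's Statistical Plan and Power, replace the statements that power will increase and be ample with the cytokine power implied by the paired t-test: 76% for IL-6 and 57% for TNF-alpha.
2. Where each document describes the model, write condition-by-time and condition-by-time-squared as the test of the stress response, or pre-specify an in-window contrast. For the first, the SAP's conditional use of time squared should become fixed. For the second, one window must be chosen, since the protocol gives both 40–90 min and one to two hours.
3. Give IL-6 and TNF-alpha power for that test over stated ranges of ρ and response profile, and say what the cited d measures.

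Simply declaring the session-mean comparison to be the condition test would be a poor remedy, since it would fix in place the contrast that dilutes a transient response.

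The cost is a little more analysis work, a short power table and a less favourable stated power for the cytokines. No new data are needed.

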Preliminary work relevant to the Aims of the proposed study: To test whether mtDNA is released in response to psychological stress, we conducted a preliminary uncontrolled laboratory study assessing levels of ccf-mtDNA before and after an acute (5-min) socio-evaluative stressor on two separate occasions. The stressor was chosen for its ability to evoke glucocorticoid hormone release and reliably stimulate increases in circulating markers of inflammation, which typically peak 1-2 hours post-stress. We developed a rigorous approach to quantify serum levels of two mtDNA genes (CYTB and ND1) in 50 healthy midlife individuals (mean age = 50 years, range: 41-58). Serum was collected at baseline (pre) and immediately (post) and 30 minutes after stress (+30 min). DNA was isolated and analyzed by a blinded operator and normalized to a standard curve.

Ccf-mtDNA levels dramatically increased +30 min after the stressor, exhibiting a large effect size ($\eta^2 = .556$, $P < 0.0001$, Figures in Research Plan), with 93% of participants showing an increase in ccf-mtDNA (CYTB). This result was replicated at a second visit, yielding similar results and a comparable effect size. Analyses of the second amplicon ND1 confirmed these findings at both sessions. Findings provide robust initial evidence for psychological stress-induced increases in the highly immunogenic molecule, ccf-mtDNA, but did not establish the time kinetics, the maximal amplitude of this response, or the association of this response with later increases in inflammatory mediators. These are gaps in our knowledge that will be examined in the proposed study.

Both mitochondrial and nuclear genomic fragments can be found in blood. Prior evidence shows that exhaustive physical exercise is followed by increases in both ccf-mtDNA and nuclear-derived ccf-nDNA, possibly due to tissue damage. To ascertain whether psychological stress-induced ccf-mtDNA could result from unspecific cellular damage and non-specific bulk cellular

material release, we also assessed two nuclear gene markers in our preliminary work. In contrast to ccf-mtDNA, ccf-nDNA (GUSB) was unchanged at +30 min on both occasions of testing. Accordingly, at +30 min after stress the ratio of circulating mitochondrial to nuclear genome mtDNA/nDNA rose by >2-fold.

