Specific Aim 1 (human stress study). Determine the temporal relationship between psychological stress, ccf-mtDNA, and systemic inflammation. We hypothesize that socioevaluative stress will trigger robust and transient ccf-mtDNA release compared to a non-stressed condition. To test this, 60 volunteers (50% female; aged 20-50) will be tested on two occasions separated by at least 1 month. On one occasion, they will be exposed to the a socio-evaluative speech stressor known to elicit increases in circulating markers of inflammation at 40-90 minutes. On the other occasion, they will rest quietly for the same period of time. Conditions will be counterbalanced across subjects and blood drawn at ten time points over two hours. We expect that the stress task will induce a specific increase in ccf-mtDNA, which will statistically mediate subsequent peak circulating IL-6 and TNF- α levels. To validate that the stress task was associated with physiological arousal, we will examine task-related changes in heart rate, blood pressure, heart rate variability, and circulating levels of cortisol, epinephrine, and norepinephrine. This study will establish the kinetics and magnitude of psychological stress-induced ccf-mtDNA release, and whether ccf-mtDNA mediates the inflammatory response to acute stress in humans.

Study Design & Methods

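### The mixed model as written has no condition-by-time term, so it cannot estimate the transient ccf-mtDNA response that Aim 1 sets out to describe

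*Protocol*

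**What the plan says.** The Protocol's Statistical Considerations make subject, and day within subject, the random effects, and state that "condition (stress/control) along with other covariates will be the fixed effects". The covariates are not named. The next sentence reads: "We will also include time and time 2 (squared) as fixed effects to allow for a nonlinear response". The SAP (Statistical Plan and Power) has the same random effects and says "condition (stress/control) will be the fixed effects". It drops the covariates and makes the quadratic term optional.

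The aims ask for more than an average difference. Specific Aim 1 hypothesises that "socioevaluative stress will trigger robust and transient ccf-mtDNA release compared to a non-stressed condition" and promises: "This study will establish the kinetics and magnitude of psychological stress-induced ccf-mtDNA release". The Scientific Background says the pilot "did not establish the time kinetics, the maximal amplitude of this response", and presents these as gaps for this trial to fill. Study Design & Methods schedules ten samples per session, at -5, 5, 10, 20, 30, 45, 60, 75, 90 and 120 minutes, chosen to show early, late and recovery changes. The power text adds that "we are collecting several measurements over time and will be modeling the entire trajectory".

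**The concern.** Time and time squared enter the model as terms shared by both sessions. They describe a curve common to stress and rest, such as diurnal drift or a catheter effect. They do not describe a curve specific to stress. Only the condition coefficient separates the sessions, and it is one number.

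Two things are at stake.

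- **Estimation.** Followed exactly, the model cannot give the size of the peak, the time to peak or the return to baseline relative to control. These are the main stated output of Aim 1.
- **Detection.** The condition coefficient averages in the pre-task sample and any samples where the response has not begun or has ended. It also carries day-to-day differences in level that a -5 min reference would remove. A short response may therefore be diluted.

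**Working it through.** **Inputs from the documents.** n = 60, each subject in both conditions; two-sided α = 0.05; ten samples per session; d = 1.13 (ccf-mtDNA, pilot), 0.35 (IL-6) and 0.28 (TNF-α).

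**The plan's own figure.** A paired t-test by the noncentral t distribution with n = 60 gives a smallest detectable d of 0.368 at 80% power. At the stated 0.38, power is 82.5%. The plan's figure is slightly conservative, and the gap does not matter here. The calculation uses one difference per subject but does not say which difference.

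**Step 1: what the model can express.** For subject i, condition C (0 or 1) and time t:

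E[Y] = β0 + β1·C + β2·t + β3·t²

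Stress minus control at time t is β1 for every t, including -5 min. This follows from the equation and needs no assumption about effect size or correlation.

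**Step 2: what β1 estimates.** The stated random effects imply equal correlation within a session. With complete data, the estimate of β1 is then the mean over subjects of (stress session mean − control session mean). A flat elevation in k of ten samples is estimated at k/10 of its size:

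- 20-45 min: 3/10 = 0.30, so 1.13 becomes 0.339
- 45-90 min: 4/10 = 0.40
- all nine post-task samples: 9/10 = 0.90

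In a simulated trial with a triangular response peaking at 1.13 at 30 min, the REML fit of the written model gave 0.301 (SE 0.101). The paired difference in session means was the same (0.301, SE 0.101). Type I error over 8,000 null simulations was 4.8%. The test is valid, but it answers a different question.

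**Step 3: illustrative power.** Assumptions not in the documents: flat responses in the windows shown, and a common correlation ρ among the ten stress-minus-control differences. The scale of d is also not given, so two are shown:

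- Scale A: d in SDs of the stress-minus-control difference at one sample.
- Scale B: d in SDs of that difference in change from -5 min, so the effect is d·√(2(1−ρ)) in scale A units.

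The standardised effect for the written test is (k/10)·effect / √((1+9ρ)/10). For the ccf-mtDNA pulse at ρ = 0.8:

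- A: 0.339/√0.82 = 0.374, power 81%
- B: effect 1.13·√0.4 = 0.715; 0.3·0.715/√0.82 = 0.237, power 44%

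The joint test is Hotelling's T² on the nine changes from -5 min (9 and 51 df). The window test compares the 45-90 min mean with -5 min. Power in %, scale A / scale B:

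| Marker and response | ρ | Written | Window | Joint |
|---|---|---|---|---|
| ccf-mtDNA, 20-45 min | 0 | >99 / >99 | – | >99 / >99 |
| | 0.5 | 94 / 94 | – | >99 / >99 |
| | 0.8 | 81 / 44 | – | >99 / >99 |
| | 0.9 | 77 / 23 | – | >99 / >99 |
| IL-6, 45-90 min | 0 | 92 / >99 | 66 / 92 | 78 / 99 |
| | 0.3 | 42 / 55 | 81 / 92 | 93 / 99 |
| TNF-α, 45-90 min | 0 | 77 / 97 | 48 / 77 | 55 / 89 |
| | 0.3 | 29 / 38 | 63 / 77 | 73 / 89 |
| IL-6, all nine post-task | 0.3 | 98 / >99 | 81 / 92 | 46 / 63 |

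For short responses at moderate or high ρ the written test loses power, sometimes heavily. For sustained responses, or ρ near zero for the cytokines, it is the strongest of the three.

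**Step 4: is condition x quadratic time enough?** A noise-free fit to a 20-45 min pulse of height 1 gives a difference of 0.14 at -5 min (true 0), 0.52 at 45 min (true 1) and about -0.29 at 120 min (true 0). The largest change from -5 min is 0.38, and the fitted peak is at about 46 min. The shape is badly wrong.

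**The case against.** The strongest reply is that this is an unwritten detail. The Protocol lists terms in prose and gives no formula, and it says the whole trajectory will be modelled. An interaction may well be intended. The stated test is valid, and for ccf-mtDNA with a short pulse its power is at least 94% on both scales up to ρ = 0.5.

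That limits how far the power figures can be pressed, but it does not supply the missing term. A stated intent adds nothing to the model. The latitude on covariance concerns correlation, not the mean curve. If the unnamed covariates included the -5 min value, the model would still give one constant difference. Descriptive summaries do not replace a model-based contrast.

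Several narrower points stand:

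- Equal weighting needs the equal correlation implied by the stated random effects. With correlation decaying exponentially (assumed ranges of 10, 30 and 60 min), the -5 min sample would get weight 0.12, 0.19 or 0.27, and the 20-45 min samples together 0.27, 0.20 or 0.15. The estimate is still one constant.
- The scale of 1.13 is unknown. The Protocol describes its source thus: "we conducted a preliminary uncontrolled laboratory study assessing levels of ccf-mtDNA before and after". If 1.13 refers to one session's change, and changes in the two sessions are independent with equal variance, it becomes 1.13/√2 = 0.80 on scale B. Written-test power at ρ = 0.5 is then 69%.
- Hotelling's test slightly understates the joint test in a structured mixed model. The sustained IL-6 case at ρ = 0.3 becomes 53% / 71% instead of 46% / 63%.
- A 2-df test of condition x quadratic time has above 99% power for the ccf-mtDNA pulse. Its failure is in shape, not detection.

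**Conclusion.** The concern holds: the model is wrong as written for Aim 1 and must be corrected. The conclusion rests on the model equation alone. A single constant difference cannot describe a transient response, its peak or its timing. The dilution to k/10 also assumes complete data and equal within-session correlation. The power figures are illustrations under assumed shapes, correlations and scales. They show that the loss can be nil or severe, and they are not the basis for the conclusion. The SAP text preceding Statistical Plan and Power could not be checked, so the finding is limited to the two statistical sections, which agree with each other on this point.

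**What to change.** - **All blood markers:** treat time as categorical (ten levels), add condition x time, and state a within-session correlation structure, which the plan already allows for.
- **ccf-mtDNA:** make the joint condition-by-time test the single test of the stress response. Report the stress-minus-control difference in change from -5 min at each post-task time as an estimate with a confidence interval, not as nine further tests.
- **IL-6 and TNF-α:** fit the same model, keep the average condition effect, and pre-state one baseline-referenced test, either joint or window. The choice is the sponsor's, since neither is best throughout. A misplaced window is costly: an IL-6 response at 60-120 min tested at 45-90 min has 57% (A) or 72% (B) power at ρ = 0.3. Say which of the two results is confirmatory and how α is handled.
- **Both documents:** use the same model statement and name any covariates.

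The cost is wording, with no new data. Fixed effects rise from 4 to 20 on 60 x 2 x 10 = 1,200 observations per marker. Power falls relative to the average-shift test if a response is sustained at low to moderate correlation, or if correlation is near zero, as the table shows. Keeping the average effect for the cytokines limits that loss.
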